5.2. Institutional Review Board

5.3 Study Objectives

Primary Objective

- a. The primary objective is to evaluate the effects of inhaled nasal sodium pyruvate (N115) in patients with confirmed COVID-19 or flu infections by determining changes in the duration of an active infection by PCR from nasal.
 Secondary Objective
- **a.** The second objective is to evaluate the ability of the inhaled nasal sodium pyruvate therapy in subjects with COVID-19 or flu infections to improve symptoms by the use of a patient diary and by collecting periodic vital signs, especially body temperature, blood pressure and pulse/Ox.

5.4. Study Design Overview

Individuals that are symptomatic for COVID19/influenza will initially be tested by Dynamic DNA Labs or Trinity Healthcare (Screening Visit). If positive for COVID19/influenza, patient will then be solicited for participation in the trial within 24 hours. After signing Informed Consent, women of child-bearing age will provide a urine sample to test for pregnancy. They will be randomly assigned to either the placebo or drug groups in a double blinded fashion and be given a data logbook, or clinical app for their phone, in which they will record the number of coughs and other flu-like symptoms they experience each day. Patients will be contacted by phone and/or sent reminders through a clinical phone app every two days to review symptoms and protocol compliance and patients will be tested via nasal swab every other day. This will continue every other day until the subject tests negative for COVID-19/ influenza (which is

defined as a 2-Log reduction in virus titer or less than 1000 copies of viral RNA) or 14 days, whichever comes first. Personnel collecting swabs will wear N95 mask and face shield, disposable examination gloves and disposable gown while collecting nasal swabs from patients. Samples will be collected outdoors, weather permitting, or in a well ventilated room in inclement weather.

6.0. The criteria for patient selection and for exclusion of patients, and an estimate of the number of patients to be studied.

6.1. Subject Selection

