6.1.1 Number of Patients to be Studied

Fifteen patients with confirmed COVID-19 infection will be enrolled in the trial in the drug group and fifteen with confirmed COVID-19 infection will be enrolled in the trial in the placebo group. An additional fifteen patients with confirmed influenza infection will be enrolled in the trial in the drug group and fifteen with confirmed influenza infection will be enrolled in the trial in the placebo group. Efforts will be made to include women and minorities. The study will be double blinded to subjects and study investigators.

6.2. Inclusion Criteria

- **6.2.1.** Individuals with a confirmed COVID-19/influenza viral infection, as determined by a qualified laboratory test. A nasal swab or saliva test analyzed by qPCR for COVID19 or rapid flu test from nasal swab for influenza.
- **6.2.2.** Individuals who agree to abstain from sexual intercourse, or agree to use condoms or vaginal diaphragms or other devices designed to prevent contraception, during the entire course of the study

6.3. Exclusion Criteria

- **6.3.1.** Viral infections other than COVID-19 or influenza.
- **6.3.2.** Clinically significant cardiac disease including uncontrolled congestive heart failure and unstable angina
- 6.3.3. Pregnancy
- **6.3.4.** Females of child bearing potential age not on adequate contraception or lactating
- **6.3.5.** Subjects receiving systemic corticosteroid treatment within one month of Screening Visit
- 6.3.6. Subjects Less than 18 years of age
- **6.3.7.** Hospitalization within last 6 months due to acute exacerbation of airway disease
- **6.3.8.** Subjects with a clinically significant abnormal chest x-ray within past 12 months
- **6.3.9.** Medication changes within one month of study entry
- **6.3.10.** Subjects who have participated in another investigation drug treatment study within the previous month.
- **6.3.11.** Subjects with a current history of alcohol or recreational drug abuse.
- **6.3.12.** Subjects who have taken dietary supplements containing pyruvate within 24 hours prior to the screening visit.

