6.4 Inclusion of Women and Minorities

Every attempt will be made to include all genders, and minorities that present with an active COVID-19 or flu infection that are not exempted due to exclusion criteria.

7.0. A Description Of The Design Of The Study, Including The Kind Of Control Group To Be Used, If Any, And A Description Of Methods To Be Used To Minimize Bias On The Part Of Subjects, Investigators, And Analysts.

7.1. Assignment Of Subject Number And Randomization

This is a placebo controlled double blinded trial. Upon enrollment, each subject will be sequentially issued a unique subject number starting at 100. Once a number has been assigned to a subject, it cannot be re-assigned to another subject. Subjects will be encouraged to complete the study, although they may withdraw at any time without prejudice. Termination will be reported to the sponsor in a timely manner. Details of the reason(s) why a subject is dropped from the study will be documented. Enrollment will continue until the number of subjects specified in the protocol has been attained. The data from all subjects that have been given a study compound will be retained for analysis.

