7.3.1. Pre-study Visit

A pre-study visit will occur and the eligibility of the subject for inclusion determined. COVID19 or influenza positive patients will sign an Informed Consent (paper or eConsent), and a list of current medications will be taken. Urine samples from child-bearing aged women will be collected and analyzed for pregnancy (or last menstrual cycle recorded). During this visit, any flu-like symptoms will be noted, temperature, Pulse/Ox and blood pressure will also be measured. During this pre-study visit, the patients are to continue with their normal therapy, if any.

7.3.2. Study Visit 1

Only COVID19 or influenza single positive subjects meeting enrollment criteria will be enrolled after review of health information collected in the pre-study visit. The correct use of the N115 sodium pyruvate nasal spray will be demonstrated to COVID-19 or influenza infected subjects, and the subjects that have been confirmed to have an infection will administer their first dose while monitored in the clinic or via telehealth. (Nasal spray can be delivered to patient at time of telehealth visit by currier). The patients will be told to spray each nostril three times, three times per day: morning, mid-day, and evening. Patients will also be instructed on filling out the Daily Data Log form or in the use of the clinical symptoms app, which will be used to record administration of the drug doses, any flu-like symptoms, and any perceived adverse events.

7.3.3 Study Visit 2 etc.

At home or on-site follow-up visits will occur every two days after Study Visit 1. During this visit, a nasal swab will be taken to determine if the patient still has an active infection. Temperature, Pulse/Ox and blood pressure will also be examined during these visits. Study monitors will review the Daily Data Log form/ Clinical app and compliance with study protocol of N115 administration will be reviewed. If needed, additional bottles of N115 nasal spray will

be delivered to the patient in the clinic or via currier.

This process of testing every two days will continue until the particular subject proves to be virus free (2 Log or greater decrease in viral RNA or less than 1000 viral RNA copies) or 14 days, whichever is first. When the patient is virus free, he/she will be excused from the study. If the subject is virus free, they will be asked to provide a second nasal swab within 24 hours to verify the negative result.

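### Entry sets no minimum nasal viral load, so a patient already below 1000 copies on Day 0 can enter the duration comparison with nothing left to shorten

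*Combined protocol and SAP*

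**What the plan says.** **Entry.** Section 6.2.1 admits "Individuals with a confirmed COVID-19/influenza viral infection, as determined by a qualified laboratory test". The permitted tests are "A nasal swab or saliva test analyzed by qPCR for COVID19 or rapid flu test from nasal swab for influenza". No copy number is given, and none of exclusions 6.3.1 to 6.3.12 concerns viral load. At Visit 1 (7.3.2), "Only COVID19 or influenza single positive subjects meeting enrollment criteria will be enrolled after review of health information collected in the pre-study visit". The first dose follows for "the subjects that have been confirmed to have an infection will administer their first dose while monitored in the clinic or via telehealth". Neither sentence mentions a titre.

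**Outcome.** The primary objective (5.3) is assessed by "determining changes in the duration of an active infection by PCR from nasal" samples. Negative is "defined as a 2-Log reduction in virus titer or less than 1000 copies of viral RNA" in 5.4, and virus free is "2 Log or greater decrease in viral RNA or less than 1000 viral RNA copies" in 7.3.3. The first limb of the rule is relative to baseline and the second is absolute. The copy count carries no unit.

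**Day 0 swab.** The testing schedule places the titre swab on Day 0, the visit of the first dose, and not at the pre-study visit. Nothing says which comes first, and nothing makes enrolment, dosing or analysis depend on the result.

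**Analysis.** Section 7.1 states: "The data from all subjects that have been given a study compound will be retained for analysis". Section 18.2 plans a repeated-measures analysis of variance with baseline as a covariate. It has no rule for a patient whose Day 0 load is already under the threshold.

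**The concern.** The entry rule and the outcome rule overlap. Entry can rest on a specimen other than the endpoint specimen (saliva), or on an assay from which the plan asks for no copy number (the rapid flu test). A patient can therefore count as infected for entry and as negative by the plan's own nasal threshold on the same day. Once in the trial, that patient needs no fall in load to be called virus free. The duration recorded reflects the visit spacing rather than the treatment.

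At stake is the sensitivity of the primary comparison. Each virus group has only 15 patients per arm, so each place taken by such a patient removes one who could have shown an effect. An uneven split between arms also moves the observed difference.

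**Working it through.** The plan states no effect size, power or event rate, so it has no figure of its own to reproduce. The check compares the two rules and then sizes the consequence under stated assumptions.

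**Inputs from the documents:** 15 per arm per virus, so 30 per virus group (6.1.1); threshold of 1000 copies or a 2-log fall (5.4, 7.3.3); swabs every 2 days (7.3.3).

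**Assumed, not in the documents:** the share p below 1000 copies on Day 0 (5%, 10%, 20%, 30%); a true mean difference of 2 days among patients above the threshold.

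**1. Fall needed to be called virus free.** For Day 0 load B, the required log10 fall is min(2, max(0, log10(B/1000))).

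| Day 0 copies | Log10 fall needed |
|---|---|
| 500 | 0 |
| 2,000 | 0.30 |
| 10,000 | 1.0 |
| 100,000 or more | 2.0 |

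At 500 copies no fall is needed. The patient is called virus free at the first follow-up swab, about Day 2, provided the load has not risen to 1000 or more.

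**2. Dilution.** Patients below the threshold have the same recorded duration in both arms, so they contribute a difference of 0. In an unadjusted comparison of means, the observed difference is 2 × (1 − p) + 0 × p.

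**3. Chance of enrolling at least one in a virus group.** 1 − (1 − p)^30.

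**4. Chance imbalance.** With the counts in the two arms independent Binomial(15, p), this is the probability that they differ by 3 or more.

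**5. Informative patients.** 30 × (1 − p).

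| Assumed p | Observed difference (true 2 days) | At least one of 30 | Arms differ by 3 or more | Informative of 30 |
|---|---|---|---|---|
| 5% | 1.9 days | 79% | 4% | 28.5 |
| 10% | 1.8 days | 96% | 12% | 27 |
| 20% | 1.6 days | 99.9% | 25% | 24 |
| 30% | 1.4 days | >99.9% | 32% | 21 |

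**6. What an imbalance of 3 is worth.** If patients above the threshold clear on average at day m and the others at Day 2, an imbalance of 3 shifts the unadjusted difference by (3/15) × (m − 2). Taking m from the scheduled visit days as an assumption, this is 0.4, 0.8 or 1.2 days for m = 4, 6 or 8. Baseline adjustment would reduce it by an unknown amount.

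**7. Power, as illustration only.** Assume a log-rank comparison, two-sided alpha 0.05, a hazard ratio of 2, and that every informative patient reaches the endpoint. Power is then Φ(√(D/4) × ln 2 − 1.96), where D is the number of informative patients. For D = 30, 27, 24 and 21 it is 47.5%, 43.7%, 39.7% and 35.5%.

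**The case against.** - **The rule is not applied on Day 0.** Sections 5.4 and 7.3.3 use it at the every-other-day follow-up tests and ask for a confirming swab. A reader might infer that such a patient has formally reached the endpoint before the first dose. The documents do not support that, since the earliest declaration is about Day 2. The narrower point stands: the declaration then needs no fall.
- **Patients should be early and actively infected.** Section 5.4 screens symptomatic people and approaches them within 24 hours of a positive result. The purpose section says nasopharyngeal swabs establish active infection, and 6.4 also refers to active infection. This may keep the share low, and nothing in the documents supports 20% or 30% in particular. None of these statements sets a threshold, however, and 6.2.1 still allows saliva and rapid tests.
- **Confirmed infection might be read as excluding anyone under 1000 copies.** The plan uses that threshold only to end follow-up, so this reading is not written anywhere.
- **The covariate in 18.2 may absorb some imbalance.** This is correct if baseline includes the Day 0 titre, which 18.2 does not say. Adjustment cannot give a duration to a patient who has none left to measure.
- **A patient sampled early may be below 1000 and rising.** Such a patient could still carry information. This is a reason to keep an analysis of all dosed patients beside the restricted one.
- **A cut at 1000 does not remove near-threshold patients.** At 2,000 copies a 0.3-log fall is enough. This stands as a limit of the fix.
- **Entry on a positive test alone could be read as biasing the trial towards one arm.** It does not. Day 0 load precedes treatment and allocation is random.

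**Conclusion.** The gap is real and follows from the text: eligibility has no load floor, and the outcome rule has an absolute limb that can be met without any fall. The consequence is dilution and chance imbalance. Its size depends on a share that cannot be found in the documents. At 5% the loss is 0.1 day on a 2-day difference, which is small beside a 2-day sampling interval. At 30% it is 0.6 day, and the informative number falls from 30 to 21 per virus. These figures assume an unadjusted comparison of means and Day 0 loads that stay below the threshold. The near-certainty of enrolling at least one such patient at shares of 10% or more shows that a rule is needed. It does not show that one patient would change the result. This is a worthwhile, cheap improvement and not a flaw that invalidates the trial.

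**What to change.** 1. State in 7.3.2 and the testing schedule that the Day 0 nasal swab is taken before the first dose.
2. Define the primary duration set in 18.2 as randomised, dosed patients whose Day 0 nasal qPCR for the enrolling virus is at or above the plan's own 1000-copy threshold. State the unit (for example per mL, per swab or per reaction). The blinded laboratory determines membership, and it is fixed before unblinding. Because membership rests on a pre-dose sample, it cannot depend on response to treatment.
3. Keep all dosed patients in the safety and secondary analyses. Report the duration analysis in all dosed patients as a sensitivity analysis, which keeps faith with 7.1. Give the number left out of the primary set by arm.

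**Cost:** a few sentences, and no new visit or assay, since the swab is already scheduled. The real price is sample size. The primary set would be about 27, 24 or 21 of 30 per virus if 10%, 20% or 30% enter below the threshold. The restriction removes the dilution but does not bring back the lost patients. For influenza, where 6.2.1 relies on a rapid test, load cannot be screened from the entry result, so the exclusion will fall after randomisation. That should be said openly in the plan.

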6.4 Inclusion of Women and Minorities

Every attempt will be made to include all genders, and minorities that present with an active COVID-19 or flu infection that are not exempted due to exclusion criteria.

7.0. A Description Of The Design Of The Study, Including The Kind Of Control Group To Be Used, If Any, And A Description Of Methods To Be Used To Minimize Bias On The Part Of Subjects, Investigators, And Analysts.

7.1. Assignment Of Subject Number And Randomization

This is a placebo controlled double blinded trial. Upon enrollment, each subject will be sequentially issued a unique subject number starting at 100. Once a number has been assigned to a subject, it cannot be re-assigned to another subject. Subjects will be encouraged to complete the study, although they may withdraw at any time without prejudice. Termination will be reported to the sponsor in a timely manner. Details of the reason(s) why a subject is dropped from the study will be documented. Enrollment will continue until the number of subjects specified in the protocol has been attained. The data from all subjects that have been given a study compound will be retained for analysis.

7.2. Randomization

The subjects will be randomized to the placebo control or N115 drug study groups.

7.3. Study Design

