18.2. Data Collection, Management, and Statistical Analysis

The data management staff at the research clinic and lab (Trinity Healthcare and Dynamic DNA Labs) will collect and manage the data. Monitoring and auditing of the data will be

conducted by a staff member of Cellular Sciences remotely.

The basic statistical analysis will be repeated measurements of Analysis of Variance using baseline measurements as a covariant per subject. Group comparisons of N115 to placebo will be analyzed by ANOVA followed by Chi Square, Fisher Exact, and other appropriate significance tests. Data will be compared to placebo controls and current publicly available matched data and observed values compared. Time dependence in viral titer reduction will also be compared. [name] will be responsible for the statistical analysis. Analysis will be performed blinded.

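### Section 18.2 has no virus term and does not say whether the primary N115–placebo comparison pools COVID-19 and influenza or is made within each virus

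*Combined protocol and SAP*

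**What the plan says.** - **Sample size (6.1.1).** Fifteen drug and fifteen placebo patients are planned with COVID-19. The section then repeats this for influenza: "An additional fifteen patients with confirmed influenza infection will be enrolled in the trial in the drug group", with a matching placebo group.
- **Objective (5.3).** One primary objective covers patients with either infection. It is to be met by "determining changes in the duration of an active infection by PCR from nasal".
- **Eligibility (7.3.2).** "Only COVID19 or influenza single positive subjects meeting enrollment criteria will be enrolled". Each patient therefore belongs to one virus group, known before allocation.
- **Allocation (5.4, 7.1, 7.2).** Section 5.4: "They will be randomly assigned to either the placebo or drug groups in a double blinded fashion". Section 7.2: "The subjects will be randomized to the placebo control or N115 drug study groups". Section 7.1: "Enrollment will continue until the number of subjects specified in the protocol has been attained". None of these gives a list, block, ratio or stratum by virus.
- **Analysis (18.2).** "The basic statistical analysis will be repeated measurements of Analysis of Variance using baseline measurements as a covariant per subject". N115 is then compared with placebo by ANOVA and further tests. Baseline is the only covariate named. Nothing says whether the two viruses are combined or analysed apart.

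**The concern.** The sample size is laid out by virus, but the analysis is not. A single objective and a single N115–placebo comparison make a pooled analysis a natural reading; four fixed cells make two separate 15:15 comparisons equally natural. The two readings carry different risks.

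- **Pooled, virus omitted.** Any difference in outcome between COVID-19 and influenza that baseline does not explain goes into the error term. The primary outcome is duration of infection, and two viruses may clear at different speeds without a matching difference at baseline.
- **Per virus.** No virus term is needed, but there are two chances of a positive result, and no rule says how they count.
- **Undecided until the results are seen.** There are then three candidate primary results: COVID-19, influenza and pooled.

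**Working it through.** **Inputs from the documents.** Four cells of 15 (6.1.1), so 4 × 15 = 60 patients, 30 per arm and 30 per virus. No alpha, power, effect size or SD is given, so 15 per arm cannot be reproduced.

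**Assumptions.** Two-sided 5%; treatment effect 0.75 within-virus SD; baseline–outcome correlation 0.5; virus difference d of 0, 0.5 or 1 SD.

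**1. Pooled comparison, allocation not by virus, baseline equal across viruses.** Residual variance is 1 − 0.5² = 0.75 with virus in the model and 0.75 + d²/4 without it. The SE is √(residual variance × 2/30), and power ≈ Φ(0.75/SE − 1.96).

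- With virus: SE = √(0.75 × 2/30) = 0.2236; 0.75/0.2236 = 3.354; power ≈ 92%.
- Without, d = 0.5: SE = √(0.8125 × 2/30) = 0.2327; ratio 3.223; power ≈ 90%.
- Without, d = 1: SE = √(1 × 2/30) = 0.2582; ratio 2.905; power ≈ 83%.

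Simulated ANCOVA (20,000 trials per setting) gives slightly lower values, as expected of a t-test with estimated coefficients. Power without / with virus:

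| Virus difference in outcome | Baseline difference | One 30:30 list | 15:15 within each virus |
|---|---|---|---|
| 0 | 0 | 90.4 / 89.8% | 90.4 / 90.3% |
| 0.5 SD | 0 | 87.9 / 89.7% | 89.1 / 90.5% |
| 1 SD | 0 | 80.7 / 90.1% | 83.7 / 90.4% |
| 0.5 SD | 0.5 SD | 89.9 / 89.8% | 90.0 / 90.3% |
| 1 SD | 1 SD | 88.6 / 90.0% | 89.1 / 90.5% |

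**2. Type I error when virus is omitted from a pooled test.** With one 30:30 list it stays at 4.9–5.1%. With cells balanced by virus, the treatment estimate is free of the virus difference but its SE is not. The SE is too wide by √(1 + 15d²/(58 × 0.75)), which is 1.04 at d = 0.5 and 1.16 at d = 1. At d = 1 the effective critical value is about 1.96 × 1.16 = 2.27, so type I error is about 2.3% (simulated 2.4%). At d = 0.5 it is 4.0%.

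**3. Days to negative.** Section 7.3.3: "This process of testing every two days will continue until the particular subject proves to be virus free", with a limit of 14 days. Durations were simulated on that two-day grid, capped at day 14, with an assumed Weibull shape of 2 and hazard ratio of 2.2, and analysed by ANOVA without baseline. Power without / with virus:

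- placebo medians 8 and 8 days: 75% / 74–75%
- 8 and 6 days: 74% / 76%
- 9 and 5 days: 63–64% / 72–73%

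**4. Multiplicity.** Two independent per-virus tests at 5%, success on either: 1 − 0.95² = 9.75%. The best of COVID-19, influenza and pooled, each at 5%: about 11–12% by simulation.

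**5. Allocation.**

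- Exactly 15:15 in one virus under simple 1:1 randomisation, with 30 patients per virus: C(30,15)/2³⁰ = 14.4%. In both viruses: 0.144² = 2.1%. With one overall 30:30 list: 20.3%.
- Missing the target costs little. A 13:17 split raises the within-virus SE by √((1/13 + 1/17)/(2/15)) = 1.009, and an 18:12 split by √((1/18 + 1/12)/(2/15)) = 1.021.
- In the table, once virus is modelled, moving from one list to 15:15 per virus adds 0.3–0.8 points of power.

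**The case against.** The strongest reply is that 6.1.1 already states the intent. Exact counts for all four cells would rarely arise unless allocation were done within virus, so 7.2 omits a method and contradicts nothing. That stands. A reader might infer that 6.1.1 and 7.2 conflict, or that unbalanced cells would seriously harm the trial; the text does not support the first, nor the arithmetic the second.

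The precision loss also needs several conditions together: the analysis is pooled, virus is left out, the viruses differ, and baseline does not carry the difference. No section says that the comparison is pooled. With baseline in the model, a 0.5 SD virus difference costs at most about 2 points. This too stands, and it limits the size of the point. But recovery through baseline is not assured: where baseline differed by 1 SD in the direction opposite to outcome, power without virus was 73–76%, against 90% with it.

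The magnitudes rest on assumed values and on single-outcome ANCOVA and ANOVA, not the repeated-measures model of 18.2. They are illustrations.

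Two readings on error rates go too far. One is that omitting virus inflates type I error in a pooled test: it is nominal or conservative. The other is that the plan commits to a 9.75% error: it never says that success on either virus will count. The risk comes from leaving this open. The blinded analysis promised in 18.2 does not close it, because a two-sided p-value can be read without knowing which arm is which.

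**Conclusion.** The point holds, and its centre is 18.2. The plan names neither a pooled nor a per-virus primary comparison and provides no virus term if the viruses are pooled.

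Under the assumptions above, omitting virus costs about 6–9 points of power at a 1 SD virus difference that baseline does not carry (81–84% against 90%). It costs 1–2 points at 0.5 SD, about 1 point at 1 SD if baseline differs equally, and nothing if the viruses do not differ. With cells balanced by virus, the 1 SD case also lowers type I error to about 2%.

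Leaving the comparison open allows a family-wise error of 9.75% if either virus may succeed at 5%, and about 11–12% with free choice among three results. These figures do not depend on the assumed effect size.

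Allocation by virus is a secondary matter. This should be corrected, but it does not invalidate the design.

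**What to change.** **In 18.2 (main change).** Include virus as a factor or stratum in every analysis that pools COVID-19 and influenza. Name one primary N115–placebo comparison before unblinding. If both per-virus comparisons are to be primary, state how alpha is shared, for example by Holm's procedure.

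**In 7.2 (secondary).** Randomise 1:1 from a separate blocked list for each virus, each list totalling 15:15, so that the cells of 6.1.1 are met by design. Block sizes are the sponsor's choice.

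**Cost.** No extra patients or visits: one model term, one or two sentences on the primary comparison, and two lists in place of one. Sharing alpha would lower the power of each per-virus test, which is a reason to settle the choice now.
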